2.0 Objectives

2.0 Study Objectives

2.1 Research Design and Methods

Our goal is to better understand the biology of breast cancer stem cells and pleural effusion formation to improve therapy of malignant pleural effusion in breast cancer patients. Based on our preclinical studies described in the background section, a clinical trial is planned to answer specific questions regarding the role of histone deacetylation and effect of its inhibition on breast patients with MPE. In this study, eligible patients with recurrent symptomatic MPE who need an indwelling pleural catheter based on MDACC algorithms for placement will have one placed and will receive 10 weeks of VPA or placebo.

The first aim is to achieve a beneficial clinical effect of VPA on patients with MPE. The specific question is if VPA alters pleural effusion re-accumulation following placement of an indwelling pleural catheter to the extent that it will enable significant shortening of time to removal of the catheter compared to placebo. Additional aims will analyze the biology of histone deacetylation inhibition in MPE and will help to develop biomarkers of activity and noninvasive monitoring to such therapy:

The second aim is to analyze the amount of daily fluid drained with therapy. Patients will be provided a daily fluid drainage diary.

The third aim is to assess radiographic and clinical correlates using standard of care testing and assessment: Chest x-ray and CT to study effect on primary tumor burden and assessment of overall survival.

Our fourth aim is to study biological correlates. We will study the level of H3 and h4 hyperacetylation and inflammatory cytokines in the effusion and in the serum at baseline and at week 2. Fluid will be collected and stored if applicable from visits at baseline, at week 2, 6, and 10. We plan to study expression of stem cell markers on cells from effusion to demonstrate inhibitory effect of VPA on these cells. Urine will be collected and stored if applicable at baseline, weeks 2, 6, and 10 for correlative studies. Finally, we will study the effect of VPA therapy on level of circulating tumor cells.

Our fifth aim is to assess drug effect on patient symptoms, dyspnea and exercise tolerance using the EuroQOL, St George's respiratory questionnare and six-minute walk test respectively.

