3.4 On-Study Evaluations

On the day of indwelling intrapleural catheter placement the patient's pleural fluid will be drained, recorded and sent for cytology review. On the day of indwelling intrapleural catheter placement patients will receive VPA or **placebo** if cytology is positive. Patients will be provided a diary to record drainage from home.

Patients will be treated for the whole period of 10 weeks, and clinical course of disease will be monitored throughout this time. (Note: evaluations may be done within \pm 7 business days of the date specified in the protocol).

Patients will initially receive daily oral VPA 15 mg/kg/day divided in three doses or placebo divided in three doses. Based on the patient's bmi, obese patient dosing will be based on the adjusted body weight calculated using the MD Anderson Clinical

Calculator Formula (<http://inside2.mdanderson.org/apps/calculators/calc1.cfm>). If the patient tolerates the reduced dose for 10 consecutive days then the VPA dose will increase to 30 mg/kg/day divided into three doses or placebo divided into three doses. The patient will be contacted by phone to assess tolerance and instruction to increase dose. Daily dose in mg will be divided by 250 mg and rounded down to a whole number of capsules to determine the number of VPA tablets or placebo tablets to be taken 3 times per day.

Evaluations may occur any time during weeks 2, 6, and 10.

- 3.4.1 Patients will document daily amount of pleural fluid drainage.
- 3.4.2 Patients will be evaluated at weeks 2, 6, and 10 with complete interim histories and physical examinations including measurement of vital signs, performance status, weight and medical history.
- 3.4.3 Patients will complete a EQ-5D and St. George's respiratory questionnaire, at weeks 2, 6, and 10 in person, via telephone or electronic media.
- 3.4.4 Blood samples for CBC with differential, platelet count, and PT/PTT/INR, serum and plasma banking, and optional CTC (if patient agrees) assessment will be collected prior to treatment and at weeks 2, 6 and 10.
- 3.4.5 Tests to measure serum electrolytes, BUN, creatinine, glucose, albumin, alkaline phosphatase, AST or ALT, LDH, total bilirubin, amylase, lipase, magnesium and ionized calcium will be performed at weeks 2, 6, and 10.
- 3.4.6 Optional urine (if patient agrees) will be collected prior to treatment and at weeks 2, 6 and 10.
- 3.4.7 Chest x-ray will be performed immediately after catheter placement and at weeks 2, 6, and 10.

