- 3.4.8 CT scan will be performed at week 10 or earlier, if clinically indicated, to determine amount of effusion and drug effect on tumor burden.
- 3.4.9 Pleural effusion will be collected at each clinic visit. Residual fluid may be stored for additional research studies (optional).

On-Study Evaluations beyond Week 10

The EQ-5D, St. George's respiratory questionnaire and the obtaining of pleural fluid samples for research purposes will cease at the end of Week 10. After the completion of 10 weeks of VPA or placebo the patient's medical record will be followed for the date of catheter removal or date of death, which ever comes first.

Study Parameters

Studies	Prior to catheter placement	Within 72 hours prior to catheter placement	Day of catheter placement	Weeks 2, 6 and 10*	Week 10	Review EMR
Physical Exam including: v/s, wt	X ³			X ³		
Medical History	X			X		
Pregnancy Test if applicable	X ^{1,3}					
Ionized Calcium	X ³					
Magnesium	X ³					
Bloodwork	X ^{2,3}			X ^{2,3}		
ECOG PS	X			X		
St. George's questionnaire	X ³			X ³		
EQ-5D	X ³			X ³		
CXR PA and LAT		X	X	X		
Patient daily documentation of pleural fluid drainage			X	X		
Patient daily documentation of VPA or placebo administration			X	X		
optional pleural fluid			X	X		
optional blood			X	X		
optional urine			X	X		
CT chest	X ⁴				X	
Serum valproic acid for grade 2 or greater AEs ⁵						
Date of pleural catheter removal or death date						X

- Serum or Urine Pregnancy test:** Required for females of child-bearing potential. Documented use of contraception, sexual abstinence, or amenorrhea for > 6 months is sufficient to document patient is not of child-bearing potential. Otherwise must be obtained prior to first dose of VPA and must be negative to enroll.
- Hematology: CBC with differential Chemistry:** Electrolytes, BUN, creatinine, glucose, albumin, alkaline phosphatase, ALT or AST, LDH, total bilirubin, amylase, lipase, magnesium and ionized calcium.
Coagulation: Prothrombin time (PT), partial thromboplastin time (PTT), and International Normalized Ratio (INR) at baseline only.
- Within 7 days of enrollment
- Baseline CT chest completed after development of effusion and within 4 weeks of enrollment.
- Draw serum valproic acid level for any grade 2 or greater adverse events.
- Evaluations may occur any time during weeks 2, 6, and 10.

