Operating Characteristics of Toxicity Monitoring Rule					
Rate of Toxicity Leading to Dose Reduction	Probability of Stopping Early	Sample Size			
		P_{25}	P_{50}	P_{75}	
0.20	0.020	40	40	40	
0.25	0.071	40	40	40	
0.30	0.205	40	40	40	
0.35	0.407	20	40	40	
0.40	0.636	15	30	40	
0.45	0.827	10	20	35	

Analysis

We will use summary statistics to describe the demographic and clinical characteristics of patients on each treatment arm.

Primary Outcome

Time to catheter removal will be measured from the date of placement of the catheter to the date it is removed. Removal of the catheter because it is no longer needed to drain the pleura will be considered an event. Removal of the catheter for other reasons will be considered competing risks. Patients who die before their catheter is removed will be considered censored on the date of death. We will use the methods described by Gooley et al. (1999) to estimate the cumulative distribution of time to catheter removal stratified by treatment arm and randomization strata.

We will use Cox (1972) proportional hazards regression to model time to catheter removal as a function of treatment arm, cytology, and lung re-expansion, as well as other potential prognostic factors, including ECOG performance status, the number of circulating tumor cells in the peripheral blood and in the pleural effusion.

Secondary Outcomes

We will use summary statistics to describe the amount of pleural fluid drainage by treatment arm, and we will use a two-sample t-test to compare treatment arms with respect to the mean amount of pleural fluid drainage. If the usual normality assumptions do not hold we will use the Mann-Whitney test to compare treatment arms with respect to the median amount of pleural fluid drainage.

We will compare treatment arms with respect to tumor burden using a Cochran-Mantel-Haenszel chi-square test stratified by concomitant therapy. Tumor burden will be assessed with chest cat scan during week 10.

We will use summary statistics to describe symptom burden dyspnea and exercise tolerance changes and dyspnea as measured by the EQ-5D and St George's respiratory questionnaire at baseline and again at weeks 2, 6, and 10. We will use repeated measures analysis of variance methods to assess differences between treatment arms with respect to QOL, dyspnea and exercise tolerance

Toxicity

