7.1 Criteria for Intrapleural Catheter Removal

If a patient experiences the following criteria:

Once the amount of daily drainage is ≤ 150 ml for three consecutive days, pleural fluid will be drained every other day. While draining every other day, if the amount of fluid increases > 150 ml, daily drainage will be restarted. If the amount of fluid drained every other day is ≤ 150 ml on three consecutive occasions (total of 6 days), patients will be evaluated clinically and with chest radiographs and the indwelling intrapleural catheter will be removed if there is no evidence of fluid reaccumulation.

Treatment failure:

A. Patients meeting the criteria below will be considered failures as they require

removal of their catheters:

- Death while catheter in place.
- Fluid loculation with a non functioning catheter that does not meet the definition of pleurodesis.
- Blockage of IPC requiring removal of the catheter. Blockage of IPC not requiring removal but use of any unblocking therapeutic manouvers will be documented as a complication but not considered as treatment failure.
- Infection - tunnel infection, empyema or systemic infection. Exit site infection

will be reported as complication but not as a treatment failure unless it progresses to tunnel infection, empyema or systemic infection.

- Intractable pain.
- Dislodged cuff requiring removal of the catheter.

B. IPC in place >180 days without meeting catheter removal criteria.

C. Any other IPC removal that does not meet the criteria established in the treatment plan.

D. Non compliance.

E. Secondary failure. Patients requiring any additional procedure to remove pleural fluid from the affected hemithorax, to alleviate respiratory symptoms during the first 6 months after IPC has been removed following the treatment plan guidelines.

Symptomatic pleural effusion was defined as the radiological presence of pleural fluid regarded as the cause of the dyspnea by the treating physician.

Time to pleurodesis was calculated as the days between IPC insertion and removal.

Adequate lung re-expansion is defined as at least 80% pleurae apposition on the affected hemithorax as determined by visual estimation on radiological studies of the chest while IPC is in place.

Unexpandable lung (non-reexpandable lung) is the inability of the lung to expand to the chest wall allowing for normal visceral and parietal pleural apposition. The lung could be trapped or entrapped.

Pleurodesis

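### The drainage comparison leaves its summary and window undefined, and the natural reading, a mean over catheter days, is cut short by low drainage itself and understates faster resolution

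*Combined protocol and SAP*

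**What the plan says.** Section 2.1 gives the goal on a daily scale: "The second aim is to analyze the amount of daily fluid drained with therapy". Secondary objective 2.3.1 is looser and speaks only of measuring the amount drained. The data come from a home diary (Section 3.4.1): "Patients will document daily amount of pleural fluid drainage".

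The analysis, in Section 6.0 under Secondary Outcomes, is "a two-sample t-test to compare treatment arms with respect to the mean amount of pleural fluid drainage". It adds: "If the usual normality assumptions do not hold we will use the Mann-Whitney test". It does not say whether a patient's amount is a total, a mean per day, a mean per drainage or a value at a visit. It sets no window and no rule for days after removal, after death, or during alternate-day drainage.

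Section 7.1 ties removal to the same variable: "Once the amount of daily drainage is ≤ 150 ml for three consecutive days, pleural fluid will be drained every other day". After three alternate-day drainages at or below the same limit, the patient is evaluated and "the indwelling intrapleural catheter will be removed if there is no evidence of fluid reaccumulation".

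The end of the diary is also open. Section 3.4 says: "After the completion of 10 weeks of VPA or placebo the patient's medical record will be followed for the date of catheter removal". The list there of what stops at week 10 names the questionnaires and the research fluid samples, but not the diary. Section 7.1 still needs drainage volumes for as long as the catheter stays in, and declares failure only beyond 180 days.

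**The concern.** How long a patient contributes drainage data depends on the drainage. A patient who dries up quickly contributes the early, high-volume days and then leaves the record. A patient who dries up slowly contributes the same high days plus a long run of lower ones. Averaging over catheter days therefore pulls the two together. The trial is designed around faster removal (median 28 against 56 days, Section 6.0), which is the kind of effect that this summary sees least well.

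At stake is the second aim. Depending on a choice that the plan leaves open, and that could be made after the data are seen, the same patients could show a clear difference in drainage or almost none.

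**Working it through.** **The plan's own figures.** There is no effect size, SD or power for drainage. The 80% power for the primary outcome reproduces approximately: with looks at 36 and 76 events, HR 2.0 and the stated nominal levels, simulation gives 79% or 84%, depending on whether the futility level is read as two-sided or one-sided.

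**Step 1: how unequal the recorded time is.** Assume exponential removal times with the plan's medians and a 70-day diary.
- Share removed by day 70 = 1 − 2^(−70/median): 1 − 2^(−1.25) = 58% for 56 days; 1 − 2^(−2.5) = 82% for 28 days.
- Mean catheter days = (median/ln 2) × share removed: 80.8 × 0.580 = 46.8; 40.4 × 0.823 = 33.3.
- With medians of 110 and 55 days: 36% and 59% removed; 56.6 and 46.5 catheter days.

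**Step 2: the limiting case.** If drainage falls exponentially from D0 to a removal level c, the mean per catheter-day is (D0 − c)/ln(D0/c). The rate of decline cancels. For D0 = 500 and c = 150 ml/day this is 350/1.204 = 291 ml/day in both arms, however much faster one arm dries. This shows the mechanism but is not the protocol's rule. The alternate-day step is nearer to 75 ml/day, which gives 425/1.897 = 224 ml/day, and real volumes are noisy.

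**Step 3: simulation with the Section 7.1 rule.** From the documents: the two-step 150 ml rule, 38 per arm, two-sided 0.05. Assumed: log-normal starting volume (median 500 ml/day, log-SD 0.5), rate of decline with median 0.034 per day (log-SD 0.7) and doubled on VPA, daily log-noise 0.3, no deaths or removals for other reasons. Median removal comes out at 65 and 36 days.

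| Per-patient summary | Placebo | VPA | Ratio | t-test power |
|---|---|---|---|---|
| Total over 70 days, zero after removal (ml) | 15,752 | 9,270 | 0.59 | 80% |
| Mean per catheter-day, first 70 days (ml) | 261 | 209 | 0.80 | 43% |
| Mean per drainage, first 70 days (ml) | 280 | 237 | 0.85 | 32% |
| Mean per catheter-day, followed to removal (ml) | 213 | 198 | 0.93 | 14% |
| Week-10 daily mean, catheters still in (ml) | 175 | 133 | 0.76 | 4% |

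The true ratio of fluid produced over 70 days is 0.60, so the 70-day total recovers it and the catheter-day means do not. In the last row only 46% and 14% of patients contribute.

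**Step 4: range.**
- Starting volumes of 500 to 800 ml/day and several decline rates, doubled on VPA: 70-day total about 70–92%; catheter-day mean within 70 days about 40–62%; followed to removal about 10–14%.
- Abrupt cessation instead of gradual decline (median removal 55 and 27 days): 72%, 33% and 21% respectively.
- VPA halves production at every time point and does not change the rate of decline: the catheter-day mean over 70 days has a ratio of about 0.52–0.56 and power of about 99% or more.
- Mann-Whitney on the same summaries: about 38–53% for the catheter-day mean against 80–87% for the total. The choice of test is not the cause.

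**The case against.** The strongest reply is that the plan never says catheter days. A mean amount may simply be the arm mean of each patient's total, objective 2.3.1 fits that reading, and a total is not masked. That is correct, so the defect is an undefined summary whose most natural form is biased towards no difference, not a written rule that is wrong. The per-day wording of Section 2.1 still points to the daily mean.

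A reader might go further and infer from the limiting case in Step 2 that the planned comparison would hide a real effect altogether, or that halving the time to dryness would be reported as no difference. The documents do not support that. Complete masking needs every patient to decline smoothly to one fixed level and to be followed to removal. Under the Section 7.1 rule with a 70-day diary, the usual result is attenuation.

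Two further replies stand. Section 1.3 argues that VPA may lower fluid production, and a proportional fall would be seen. Time to removal is itself the primary outcome, so an effect on speed would not be lost to the trial.

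What does not stand is that a total makes the issue harmless. An unqualified total scores a patient who dies early, or loses the catheter to infection, as low drainage. In the preliminary series only 29 of 58 patients had the catheter removed because it was no longer needed.

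**Conclusion.** The concern holds as attenuation and an open choice, not as certain masking. If the summary is a mean over catheter days and VPA acts by speeding resolution, power falls from about 70–92% for a 70-day total to about 33–62% within 70 days. If catheter days are followed to removal, it falls to about 10–14% under a doubled rate of decline (21% under abrupt cessation).

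These figures rest on assumed starting volumes, spread, noise and decline, because the documents give none, and on no deaths or other removals. The direction needs less: only that low drainage ends the record and that treatment changes how soon that happens. The outcome is secondary, and the primary analysis and its power are unaffected. It should still be settled before unblinding.

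**What to change.** Define the outcome in the SAP as volume drained over a fixed window, days 1–70 from placement, as a total or divided by 70. Volume over a fixed window also removes the question of how to treat alternate-day drainage.
- Count zero for days after removal for resolved effusion, but add any fluid removed by later procedures in the window. Section 7.1 foresees such procedures under secondary failure.
- Adjust for the volume drained at placement and for the randomisation strata (lung re-expansion, ECOG status).
- Do not count days after death, or after removal for other reasons, as zero. State one convention for them, and add a rank-based sensitivity analysis that places deaths worst.

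The cost is small: SAP wording, programming on diary data already planned, and recording of later-procedure volumes up to day 70. There are two drawbacks. The convention for deaths and other removals is a choice that must be defended. The zeros after removal also make the outcome overlap partly with the primary endpoint, so it should be read as supportive and not as independent confirmation.

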2.3 Secondary Objectives

- 2.3.1 Measure the amount of pleural fluid drainage.
- 2.3.2 Study expression of inflammatory cytokines using the Luminex platform and the degree of H3 and H4 hyperacetylation in serum and pleural effusion cells.
- 2.3.3 Evaluate the effect of the study agent on tumor burden with chest CTs.
- 2.3.4 Evaluate the effect of the study agent on symptom burden, dyspnea and exercise tolerance
- 2.2.5 Measure level of circulating tumor cells in peripheral blood and pleural effusion.
- 2.2.6 Study expression of cancer stem cell markers on tumor cells in pleural effusion.
- 2.2.7 Record treatment related toxicity.
- 2.2.8 Record overall survival
- 2.2.9 Obtain urine samples for correlative studies

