3.3 Pretreatment Evaluations

Patients deemed to require catheter placement based on standard of care algorithms and gleaned from the Electronic Medical Record, will be screened for protocol eligibility. (See Section 4.0) When medically appropriate, catheters will be placed as per standard of care by a pulmonologist or their trained designee after signing the usual consent for this procedure. Monitoring will be standard of care as directed by the MD responsible for placing the catheter.

Unless otherwise noted, labs, physical exams, and screening are to be performed within 7 days of enrollment. Imaging studies are to be performed within 30 days of enrollment.

- 3.3.1 Sign an informed consent.
- 3.3.2 Complete physical exam, including measurement of vital signs, performance status, weight and medical history
- 3.3.3 Pretreatment laboratory tests:
 - **Hematology:** CBC with differential
 - **Chemistry:** Electrolytes, BUN, creatinine, glucose, albumin, alkaline phosphatase, ALT or AST, LDH, total bilirubin, amylase, lipase, magnesium and ionized calcium.
 - **Coagulation:** Prothrombin time (PT), partial thromboplastin time (PTT), and International Normalized Ratio (INR).
 - **Serum or Urine Pregnancy test:** Required for females of child-bearing potential. Documented use of contraception, sexual abstinence, or amenorrhea for > 6 months is sufficient to document patient is not of child-bearing potential. Otherwise must be obtained prior to first dose of VPA and must be negative to enroll.
- 3.3.4 EQ-5D and St. George's respiratory questionnaire
- 3.3.5 Chest x-ray within 72 hours prior to catheter placement.
- 3.3.6 Chart will be reviewed for re-staging CT scan of the chest. One will be ordered if not performed since the development of the effusion.

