Patients will be randomized to active treatment or control stratified by lung re-expansion ($\geq 80\%$ lung re-expansion, $<80\%$ lung re-expansion), ECOG performance status (0-1, 2, 3), using the Clinical Trial Conduct website (<https://biostatsitics.mdanderson.org/ClinicalTrialConduct>), which is housed on a secure server at MDACC and maintained by the MDACC Department of Biostatistics. Access to the website will be gained through usernames and passwords provided by the MDACC Department of Biostatistics to personnel responsible for enrolling patients and reviewing and analyzing patient data. Training on the use of the Clinical Trial Conduct website to randomize and enroll patients on the study will be provided by the study statistician. Investigation Pharmacy will have access the Clinical Trial Conduct website

to review the patient assignment. The IND office will be notified if an event occurs leading to the un-blinding of the randomization.

Toxicity Monitoring

We will use the methods described by Thall et al. (1995) to monitor the rate of toxicity leading to dose reduction for patients on active treatment. Because the study is blinded to the investigators, the study statistician will monitor the toxicity monitoring rule for the active treatment arm. Toxicity data leading to dose reduction will be forwarded to the study statistician as they accrue in the form of an email with the patient study identifier and a description of the toxicity leading to dose reduction.

If the rate of toxicity leading to dose reduction for patients on active treatment is more than 25% the study will be stopped. We will enroll a minimum of 10 and a maximum of 40 patients on active treatment. We will stop the study early if $P(\text{toxicity leading to dose reduction for patient on active treatment} > 25\% | \text{data from the study}) > 0.975$. That is, given the toxicity outcomes from the patients on active treatment, if we determine that there is more than a 97.5% chance that the rate of toxicity leading to dose reduction is more than 25% we will stop the study. This decision rule gives the following stopping rule. We assume a uniform prior distribution for the rate of toxicity leading to dose-reduction. Stop the study if

[# of pts on active treatment with toxicity leading to dose reduction / # of pts evaluated]
> 6/10, 8/15, 9/20, 11/25, 13/30, 14/35, 16/40

The operating characteristics of this study design are shown in the table below.

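### The tumour-burden comparison specifies no use of the baseline chest CT or of the randomisation strata, which costs precision and leaves a chance baseline imbalance uncorrected

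*Combined protocol and SAP*

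**What the plan says.** The objective in section 2.3 is: "Evaluate the effect of the study agent on tumor burden with chest CTs". The whole analysis is two sentences in section 6.0, Secondary Outcomes: "We will compare treatment arms with respect to tumor burden using a Cochran-Mantel-Haenszel chi-square test stratified by concomitant therapy", followed by "Tumor burden will be assessed with chest cat scan during week 10". Tumour burden is not defined as a variable, and no baseline value, change score or response category is named.

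A baseline scan is secured for everyone. Section 3.3 has the chart reviewed for a chest CT and adds: "One will be ordered if not performed since the development of the effusion". The footnote to the Study Parameters table in section 3.4 reads: "Baseline CT chest completed after development of effusion and within 4 weeks of enrollment".

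The follow-up scan is timed differently in section 3.4: "CT scan will be performed at week 10 or earlier, if clinically indicated, to determine amount of effusion and drug effect on tumor burden".

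On allocation, section 6.0 says: "Patients will be randomized to active treatment or control stratified by lung re-expansion", with ECOG performance status (0-1, 2, 3) as the second factor. Neither factor appears in the tumour-burden test.

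**The concern.** An objective about the agent's effect on tumour burden calls for a comparison that accounts for how much tumour each patient had at entry. Patients with metastatic disease will differ widely at entry, and each patient's week-10 burden will depend partly on where it started. If that is not adjusted for, between-patient variation stays in the error term, and an imbalance that arises by chance carries through to the week-10 difference.

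The omission is not the plan's general habit. Section 6.0 describes the questionnaires at baseline and at weeks 2, 6 and 10, and assesses circulating tumour cells and percent quiescent cells as change from baseline. For the quiescence marker it gives baseline variation as the reason for a relative criterion. The primary outcome's cumulative distribution is estimated by arm and randomisation strata. For tumour burden neither device is mentioned.

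The timing of the one stratifying variable that is named, concomitant therapy, is also not given. If it meant therapy chosen during the 10 weeks, it could itself be affected by treatment.

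**Working it through.** **The plan's own figure.** None exists for tumour burden: no power, effect size or error rate is stated. The 76 patients and 80% power in section 6.0 belong to time to catheter removal. Only the patient numbers are used here.

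**Inputs from the documents.** 76 patients, 38 per arm (section 6.0). Median survival 7.4 months in breast cancer with malignant pleural effusion (section 1.1).

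**Assumptions.** Exponential survival. Deaths unrelated to arm. A continuous burden measure scaled to SD 1. Baseline-to-week-10 correlation r, which the documents do not give, shown from 0.3 to 0.9.

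**Step 1, scans at week 10.** 10 weeks = 70 days = 70/30.44 = 2.30 months. Proportion alive = exp(-ln 2 × 2.30/7.4) = 0.806. Then 76 × 0.806 = 61 patients, and 38 × 0.806 = 30.6, about 31 per arm.

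**Step 2, chance imbalance at baseline.** The difference in baseline means has standard error √(2/n) in SD units: 0.229 at n = 38 and 0.254 at n = 31. P(|imbalance| > d) = 2[1 - Φ(d/SE)].

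| d | 38 per arm | 31 per arm |
|---|---|---|
| 0.3 SD | 19% | 24% |
| 0.5 SD | 2.9% | 4.9% |

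**Step 3, effect on the week-10 difference.** With no drug effect, an imbalance d shifts the expected week-10 difference by r × d. For d = 0.3 the shift is 0.09, 0.15, 0.21 or 0.27 SD at r = 0.3, 0.5, 0.7 or 0.9.

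The false-positive rate of an unadjusted two-sided 5% test, given the imbalance, uses residual SE √(1 - r²) × √(2/n) and critical value 1.96 × √(2/n). At 31 per arm:

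| r | given no imbalance | given 0.3 SD | given 0.5 SD |
|---|---|---|---|
| 0.3 | 4.0% | 5.4% | 7.9% |
| 0.5 | 2.4% | 5.9% | 13% |
| 0.7 | 0.6% | 5.6% | 21% |
| 0.9 | 0.0% | 2.0% | 33% |

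The rate is below 5% in well-balanced trials and above it in badly imbalanced ones. Averaged over randomisations it is 5.0%.

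**Step 4, what adjustment gains.** The variance removed is r²: 9%, 25%, 49% or 81%. For an assumed true difference of 0.5 SD, power is about Φ(0.5/[√(1 - r²) × √(2/n)] - 1.96).

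| r | 31 per arm, unadjusted | 31 per arm, adjusted | 38 per arm, unadjusted | 38 per arm, adjusted |
|---|---|---|---|---|
| 0.3 | 50% | 54% | 59% | 63% |
| 0.5 | 50% | 62% | 59% | 71% |
| 0.7 | 50% | 79% | 59% | 86% |
| 0.9 | 50% | 99% | 59% | 99.9% |

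**Step 5, the planned type of test.** CMH needs categories, so week-10 burden was dichotomised and stratified by an assumed two-level concomitant therapy (40,000 simulated null trials, 38 per arm). Overall type I error was 5.0% to 5.1%. In trials with a baseline imbalance above 0.3 SD it was 9.0%, 12.6% or 18.3% at r = 0.5, 0.7 or 0.9. Adding a baseline high/low stratum brought these to 5.8%, 6.0% and 6.1%.

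**Step 6, can CMH carry all the factors?** Lung re-expansion (2) × ECOG (3) gives 6 strata. A two-level concomitant therapy makes 12, and a two-level baseline burden makes 24. That leaves 61/24 = 2.5 patients per stratum, too sparse for CMH.

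**The case against.** The strongest reply is that the text does not say raw week-10 values are compared. It says when the scan is done. A CMH test needs categories, and a response category relative to the baseline scan would fit it. The objective speaks of scans in the plural, and section 3.4 says the follow-up CT is meant to show drug effect on tumour burden. That stands: a reader might infer that the baseline scan is deliberately ignored, but this rests on silence. What the documents support is that its use is not specified.

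Three other readings go further than the text allows.

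- **A false drug effect is likely.** Randomisation holds the overall error rate at 5%, and an imbalance above 0.5 SD is uncommon (4.9% of trials at 31 per arm). The harm is conditional bias and lost power.
- **Leaving out lung re-expansion and ECOG creates a spurious effect.** Allocation is stratified on them, and neither measures tumour burden. If they are prognostic, omitting them tends to make the test conservative.
- **Concomitant therapy is recorded after randomisation.** Section 6.0 does not say. Section 5.1.6 refers to patients already on hormonal or systemic chemotherapy at eligibility, which would be a baseline status, and blinding limits arm-dependent choice of therapy. Stratifying by anticancer therapy is reasonable for this outcome; only its timing needs stating.

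It is also fair to say that the gain is modest if r is low, and that scans taken before week 10 could raise the number available above 31 per arm.

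**Conclusion.** The point holds in this form: the planned test specifies no use of a baseline CT that every patient has, nor of the factors used to randomise. It therefore gives up precision and leaves any chance imbalance in burden uncorrected. On either reading of the categories, the outcome variable and the role of the baseline scan are undefined, so the choice could be made after the data are seen.

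The size depends on a correlation the documents do not supply: from 9% of variance at r = 0.3 to 81% at r = 0.9. The count of about 31 per arm rests on exponential survival at the 7.4-month median. The variance and power figures apply to a continuous measure; the simulation shows the same direction for a categorical test. This is worth correcting, but it concerns one secondary outcome and leaves the primary conclusion unaffected.

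**What to change.** In section 6.0, Secondary Outcomes:

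1. Define tumour burden relative to the baseline CT, either as a measured change or as a response category.
2. Compare arms with adjustment for baseline burden, lung re-expansion and ECOG. Use ANCOVA for a measured outcome or ordinal regression for a response category, because crossing all the factors as CMH strata would be too sparse.
3. If concomitant therapy is kept, use the status recorded before randomisation and say so.
4. Reconcile the scan timing in section 6.0 with that in section 3.4, and state how a scan taken before week 10 enters the analysis.
5. Report deaths before the scan and missing scans by arm, with a stated rule for handling them.

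The cost is analysis-plan wording. Both scans are already scheduled, so no patient or visit is added.
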